## 5.2. Exclusion Criteria

Subjects who meet any of the following criteria will be disqualified from entering the study:

1. Any previous or current histologic or cytologic evidence of small cell OR combined small cell/non-small cell disease in the archival tumor tissue or pretreatment tumor biopsy.
2. Any history of interstitial lung disease (including pulmonary fibrosis or radiation pneumonitis), has current interstitial lung disease (ILD), or is suspected to have such disease by imaging during Screening.
3. Clinically severe respiratory compromise (based on Investigator's assessment) resulting from intercurrent pulmonary illnesses including, but not limited to:
  - a. Any underlying pulmonary disorder (eg, pulmonary emboli within 3 months prior to the study enrollment, severe asthma, severe chronic obstructive pulmonary disease [COPD], restrictive lung disease, pleural effusion);
  - b. Any autoimmune, connective tissue or inflammatory disorders with pulmonary involvement (eg, rheumatoid arthritis, Sjogren's syndrome, sarcoidosis);**OR** prior complete pneumonectomy.
4. Is receiving chronic systemic corticosteroids dosed at >10 mg prednisone or equivalent anti-inflammatory or any form of immunosuppressive therapy prior to enrollment. Subjects who require use of bronchodilators, inhaled or topical steroids, or local steroid injections may be included in the study.
5. Evidence of any leptomeningeal disease
6. Evidence of clinically active spinal cord compression or brain metastases, defined as untreated and symptomatic, or requiring therapy with corticosteroids or anticonvulsants to control associated symptoms. Subjects with clinically inactive or treated brain metastases who are asymptomatic (ie, without neurologic signs or symptoms and not requiring treatment with corticosteroids or anticonvulsants) may be included in the study. Subjects must have a stable neurologic status for at least 2 weeks prior to Cycle 1 Day 1.
7. Inadequate washout period prior to Cycle 1 Day 1, defined as:
  - a. Whole brain radiation therapy <14 days or stereotactic brain radiation therapy <7 days;

- b. Any cytotoxic chemotherapy, investigational agent or other anticancer drug(s) from a previous cancer treatment regimen or clinical study (other than EGFR TKI), <14 days or 5 half-lives, whichever is longer;
  - c. Monoclonal antibodies, other than immune checkpoint inhibitors, such as bevacizumab (anti-VEGF) and cetuximab (anti-EGFR) <28 days;
  - d. Immune checkpoint inhibitor therapy <21 days;
  - e. Major surgery (excluding placement of vascular access) <28 days;
  - f. Radiotherapy treatment to more than 30% of the bone marrow or with a wide field of radiation <28 days or palliative radiation therapy <14 days; or
  - g. Chloroquine/hydroxychloroquine  $\leq$ 14 days.
8. Prior treatment with an anti-HER3 antibody or single-agent topoisomerase I inhibitor.
  9. Prior treatment with an ADC that consists of any topoisomerase I inhibitor.
  10. Has unresolved toxicities from previous anticancer therapy, defined as toxicities (other than alopecia) not yet resolved to National Cancer Institute Common Terminology Criteria for Adverse Events (NCI-CTCAE) v5.0, Grade  $\leq$ 1 or baseline. Subjects with chronic Grade 2 toxicities may be eligible at the discretion of the Investigator after consultation with the Sponsor Medical Monitor or designee.
  11. Has history of other active malignancy within 3 years prior to enrollment, except:
    - a. Adequately treated non-melanoma skin cancer;
    - b. Superficial bladder tumors (Ta, Tis, T1);
    - c. Adequately treated intraepithelial carcinoma of the cervix uteri;
    - d. Low risk non-metastatic prostate cancer (with Gleason score <7, and following local treatment or ongoing active surveillance);
    - e. Any other curatively treated in situ disease.
  12. Uncontrolled or significant cardiovascular disease prior to Cycle 1 Day 1, including:
    - a. QT interval corrected with Fridericia's formula (QTcF) prolongation interval of >470 ms for females and >450 ms for males;
    - b. Left ventricular ejection fraction (LVEF) <50% by either ECHO or MUGA scan;
    - c. Resting systolic blood pressure >180 mmHg or diastolic blood pressure >110 mmHg;
    - d. Myocardial infarction within 6 months;
    - e. New York Heart Association (NYHA) Classes 2 to 4 congestive heart failure (See Section 10.3.2) within 28 days;
    - f. Uncontrolled angina pectoris within 6 months;
    - g. Cardiac arrhythmia requiring antiarrhythmic treatment.
  13. Active hepatitis B and/or hepatitis C infection, such as those with serologic evidence of viral infection within 28 days of Cycle 1 Day 1.
    - a. Subjects with past or resolved HBV infection are eligible if:
      - i. Hepatitis B surface antigen (HBsAg) negative and hepatitis B core antibody (anti-HBc) positive; **OR**
      - ii. HBsAg positive and HBV DNA viral load is documented to be  $\leq$ 2000 IU/mL in the absence of anti-viral therapy and during the previous 12 weeks prior to

- the viral load evaluation with normal transaminases values (in the absence of liver metastasis); **OR**
- iii. HBsAg positive and HBV DNA viral load is documented to be  $\leq 2000$  IU/mL in the absence of anti-viral therapy and during the previous 12 weeks prior to the viral load evaluation for subjects with liver metastasis and abnormal transaminases with a result of AST/ALT  $< 3 \times$  ULN.
  - b. Subjects with a history of hepatitis C infection will be eligible for enrollment only if the viral load according to local standards of detection is documented to be below the level of detection in the absence of anti-viral therapy during the previous 12 weeks (ie, sustained viral response according to the local product label but no less than 12 weeks, whichever is longer).
- 14. Subject with any human immunodeficiency virus (HIV) infection.
  - 15. Any evidence of severe or uncontrolled diseases including active bleeding diatheses, active infection, psychiatric illness/social situations, geographical factors, substance abuse, or other factors which in the Investigator's opinion makes it undesirable for the subject to participate in the study or which would jeopardize compliance with the protocol. Screening for chronic conditions is not required.
  - 16. History of hypersensitivity to either the drug substance or any excipients in patritumab deruxtecan.
  - 17. Female who is pregnant or breast-feeding or intends to become pregnant during the study.
  - 18. Prior or ongoing clinically relevant illness, medical condition, surgical history, physical finding, or laboratory abnormality that, in the Investigator's opinion, could affect the safety of the subject; alter the absorption, distribution, metabolism or excretion of the study drug; or confound the assessment of study results.
  - 19. Has clinically significant corneal disease.

### **5.3. Screening Failures, Rescreening, and Subject Replacement**

The study will allow rescreening once for any subject who failed to meet eligibility criteria upon initial Screening or whose Screening window has elapsed. The Investigator will consult with the Sponsor prior to making the decision to rescreen a subject. A unique subject identification number will be assigned at the time of rescreening. The initial reason why the subject is ineligible for the initial evaluation will be recorded on the Screening Log at the site and will be entered into the clinical database. If a subject undergoes rescreening, the subject must repeat all out of window assessments (ie, procedures performed beyond the specified window prior to Cycle 1 Day 1).

## 6. STUDY TREATMENT(S)

See [Figure 1.1](#) for treatment sequence.

### 6.1. Study Drug(s) Description

[Table 6.1](#) describes the formulation, dose, regimen, duration, packaging, and labeling of patritumab deruxtecan (U3-1402).

**Table 6.1: Study Drug Dosing Information**

Study Drug Name	Patritumab Deruxtecan (U3-1402) for Injection 100 mg
Dosage Formulation	Patritumab deruxtecan (U3-1402) drug product will be provided as 100 mg of lyophilized-drug powder (Lyo-DP) in single-use amber glass vials of sterile drug product to be reconstituted with 5 mL water for injection to 20 mg/mL prior to use.
Dosage Level(s)	Fixed dose regimen: 5.6 mg/kg Up-titration dose regimen: Cycle 1: 3.2 mg/kg; Cycle 2: 4.8 mg/kg; Cycle 3 and subsequent cycles: 6.4 mg/kg
Route of Administration	Intravenous (IV)
Dosing	One IV infusion every 3 weeks on Day 1 of each 21-day cycle
Duration	Patritumab deruxtecan (U3-1402) will be infused as a continuous IV infusion over approximately 90 minutes on Day 1 of Cycle 1. In the absence of infusion-related reaction (IRR), the subsequent doses will be infused over approximately 30 minutes. In case of IRR at any time during treatment, subsequent doses will be infused over 90 minutes.
Packaging	Patritumab deruxtecan (U3-1402) will be supplied by the Sponsor. Study drug will be packaged in cartons containing 1 vial of patritumab deruxtecan for Injection 100 mg (lyophilized powder). Each vial is single use only.
Labeling	Patritumab deruxtecan (U3-1402) packaging will be labeled as required per local regulatory requirement.

### 6.2. Preparation, Handling, Storage, and Accountability for Study Drug(s)

#### Preparation, Handling, and Disposal

The preparation of study drug will be conducted in accordance with the Dose Preparation Instructions in the Pharmacy Manual provided by the Sponsor.

Prepared medicinal solutions should be used immediately. Refer to the Dose Preparation Instructions for detailed information about preparation and administration of patritumab deruxtecan.

Procedures for proper handling and disposal of anticancer drugs should be followed in compliance with the standard operating procedures (SOPs) of the site.

#### Administration

The selected dose of patritumab deruxtecan will be reconstituted with 5 mL water for injection to 20 mg/mL prior to use. Following the reconstitution in 5 mL water for injection the product will be diluted in 5% dextrose solution for infusion. Patritumab deruxtecan will be administered as a continuous IV infusion over approximately 90 minutes on Day 1 of Cycle 1. If there are no

infusion-related reactions after the initial dose, subsequent doses of patritumab deruxtecan will be infused over approximately 30 minutes on Day 1 of each subsequent cycle Q3W. Refer to [Table 6.4](#) for additional information on drug administration following infusion-related reactions.

Subjects should receive the study drug within 3 days of randomization/enrollment. The subject's weight at baseline (defined as the last measurement on or prior to Cycle 1 Day 1) will be used to calculate the initial dose. The subject's weight will be determined at the beginning of each cycle. If during Cycle 1 Day 1 or throughout the course of treatment, the subject's weight changes by  $\geq 10\%$  from the baseline weight, the dose will be recalculated using this new weight and will be considered the new baseline for all subsequent dosing calculations.

The drug formulation used in this study will be Lyo-DP.

### **Storage**

Patritumab deruxtecan vials must be stored in a secure, limited access storage area under the recommended storage conditions noted on the label and protected from light: Lyo-DP should be stored at  $5^{\circ}\text{C} \pm 3^{\circ}\text{C}$  (between  $2^{\circ}\text{C}$  and  $8^{\circ}\text{C}$ ).

If storage conditions are not maintained per specified requirements, then the Sponsor or contract research organization (CRO) should be contacted.

See the Pharmacy Manual for additional information on storage conditions of the study drug.

### **Drug Accountability**

When a drug shipment is received, the Investigator or designee will check the amount and condition of the drug against the shipping documentation.

The Receipt of Shipment Form should be faxed as instructed on the form unless receipt is controlled by interactive response technology (IRT). The original will be retained at the study site.

In addition, the Investigator or designee shall contact the Sponsor as soon as possible if there is a problem with the shipment.

The Investigator is responsible for study drug accountability, reconciliation and record maintenance (ie, Receipt of Shipment Form, dispensation/return record, and certificate of destruction/return receipt).

At the end of the study or as directed, all unused, used and/or partially used patritumab deruxtecan will be destroyed at the site as per site policy or local laws (and documented). As applicable, the study site must file a copy of the appropriate institution policy (and certificate of destruction) within their Investigator site file and provide a copy to the Sponsor. Please see the Pharmacy Manual for details.

## **6.3. Measures to Minimize Bias: Randomization and Blinding**

### **Method of Treatment Allocation**

This will be an open-label study. Initially, subjects will be randomized to one of the 2 arms (5.6 mg/kg fixed dose regimen [Arm 1] or up-titration dose regimen [Arm 2]) in a 1:1 ratio until

a decision is made based on data from the U31402-A-U102 study to continue enrollment in Arm 1, Arm 2, or in both arms. A maximum of 3 days is allowed between randomization and Cycle 1 Day 1 of the treatment in the study.

An independent biostatistician from the CRO, not otherwise part of the Sponsor study team, will generate the randomization list. Based on this information, the system will assign a unique randomization number and dose group for that subject.

Overall enrollment will be managed through the IRT for subjects meeting all eligibility criteria. The instructions on how to use the system will be provided in the IRT Manual.

### **Blinding**

This is an open-label study; therefore, no blinding will be used.

## **6.4. Treatment Compliance**

Patritumab deruxtecan will be administered as an IV infusion to subjects under the supervision of study site personnel. Therefore, treatment compliance will be guaranteed as long as the subject attends each visit for administration of study drug. Start and stop date/time of injection and amount of drug administered must be recorded in the electronic case report form (eCRF).

## **6.5. Guidelines for Dose Modification**

All dose modifications (ie, dose interruption, dose reduction, and/or treatment discontinuation) should be based on the worst preceding toxicity (NCI-CTCAE v5.0). Possible exceptions to the dose modification criteria may be allowed on a case-by-case basis after discussion and agreement between the Investigator and Sponsor. The agreement must be documented. Dose modification decisions may be based on local laboratory results.

All dose modifications must be recorded on the adverse event (AE) and drug administration eCRF pages. If study drug is interrupted, missed doses will not be made up.

Dose modifications are applicable only to TEAEs that are assessed as related to use of patritumab deruxtecan by the Investigator(s). For non-drug related TEAEs, follow standard clinical practice. Appropriate clinical experts should be consulted as deemed necessary.

### **Dose Delay Guidelines**

The dose can be delayed for up to 28 days from the planned date of administration (ie, 49 days from the last infusion date). If a subject is assessed as requiring a dose delay longer than 28 days, the subject should be discontinued from the study treatment.

### **Dose Reduction Guidelines**

If dose reduction is required, patritumab deruxtecan dosing should be reduced by 1 dose level at a time ([Table 6.2](#)). Once the dose of patritumab deruxtecan has been reduced due to an AE, all subsequent cycles should be administered at that lower dose level unless further dose reduction is required.

Dose reductions for the fixed dose 5.6 mg/kg regimen are described in [Table 6.2](#).

**Table 6.2: Dose Reductions for the Fixed Dose 5.6 mg/kg Regimen**

Starting Dose (0)	5.6 mg/kg IV infusion Q3W
Dose Level (- 1)	4.8 mg/kg IV infusion Q3W
Dose Level (- 2)	3.2 mg/kg IV infusion Q3W

IV = intravenous; Q3W = every 3 weeks.

In the up-titration regimen, subjects will undergo up-titration as follows: Cycle 1 at 3.2 mg/kg, Cycle 2 at 4.8 mg/kg, Cycle 3 and subsequent cycles at 6.4 mg/kg Q3W. The recommended dose reduction is described in [Table 6.3](#). If a TEAE requiring dose reduction occurs during up-titration (ie, Cycles 1 or 2), a further increase in dose is prohibited.

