The **up-titration dose regimen** was additionally chosen for study based on data collected in the U31402-A-J101 study that demonstrated preliminary evidence of a favorable safety profile at this dose regimen. During the U31402-A-J101 dose escalation, Grade 3 or 4 thrombocytopenia was observed most often in Cycle 1 followed by a reactive thrombocytosis over Cycle 2 and Cycle 3 resulting in a pre-infusion Cycle 3 platelet count equal to or greater than baseline (Screening). The incidences of both  $\geq$ Grade 3 thrombocytopenia and ( $\geq$ Grade 3 neutropenia increased with respect to administered dose, and exposure-response analyses showed that probability of either of these events correlated with the Cmax of the drug payload (MAAA-1181a). Furthermore, the payload Cmax was noted to be higher in Cycle 1 versus Cycle 3. Based on these preliminary observations, an up-titration dose regimen was chosen for study in the U31402-A-J101 study, whereby 3.2 mg/kg is administered in Cycle 1, 4.8 mg/kg in Cycle 2, and 6.4 mg/kg in Cycle 3 and beyond, in 3-week cycles. This is based on the hypothesis that starting with a lower dose in Cycle 1 would be associated with a lower payload

Cmax and hence a lower risk of ≥Grade 3 thrombocytopenia or neutropenia during Cycle 1, and that reactive thrombocytosis and decreases in payload Cmax over Cycles 2 and 3 might present a lower risk of ≥Grade 3 thrombocytopenia or neutropenia in later cycles.

As of 05 Aug 2019, the up-titration dose regimen in the U31402-A-J101 study has shown an incidence of ≥Grade 3 thrombocytopenia in 16.7% of subjects; whereas, the 4.8 mg/kg or 6.4 mg/kg fixed dose regimens was 24.4% and 53.5%, respectively (Table 4.2). In addition, ≥Grade 3 neutropenia was observed in 50.0% of subjects treated with the up-titration dose regimen compared to 22.2% and 48.8%, respectively, in the 4.8 mg/kg or 6.4 mg/kg fixed dose regimens.

Based on this preliminary evidence, both a fixed dose regimen and an up-titration dose regimen are being evaluated in the present study to provide a deeper understanding of the safety and efficacy of both regimens.

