**Table 6.3: Dose Reductions for the Up-titration Dose Regimen**

Starting Dose (0)	6.4 mg/kg IV Q3W	4.8 mg/kg Q3W	3.2 mg/kg Q3W
Dose Level (- 1)	4.8 mg/kg IV Q3W	3.2 mg/kg Q3W	Discontinue
Dose Level (- 2)	3.2 mg/kg IV Q3W	Discontinue	Discontinue

IV = intravenous; Q3W = every 3 weeks.

Subjects will be withdrawn from the study treatment if further toxicity meeting the requirement for dose reduction occurs.

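### For a Cycle 1 toxicity requiring dose reduction in the up-titration arm, Section 6.5 and Table 6.3 leave it unclear whether the subject continues or stops

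*Combined protocol and SAP*

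**What the plan says.** Section 6.5, Dose Reduction Guidelines, opens with a general rule for both arms: "patritumab deruxtecan dosing should be reduced by 1 dose level at a time". The only table cited there is Table 6.2, which covers the fixed-dose arm.

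The text after Table 6.2 turns to Arm 2. It sets the schedule, "Cycle 1 at 3.2 mg/kg, Cycle 2 at 4.8 mg/kg, Cycle 3 and subsequent cycles at 6.4 mg/kg Q3W", then points to Table 6.3 with the words "The recommended dose reduction is described in", and then adds: "If a TEAE requiring dose reduction occurs during up-titration (ie, Cycles 1 or 2), a further increase in dose is prohibited".

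Table 6.3 has three columns, each headed by a dose at level 0 and none by a cycle:

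| Level | Column 1 | Column 2 | Column 3 |
|---|---|---|---|
| 0 | 6.4 mg/kg | 4.8 mg/kg | 3.2 mg/kg |
| -1 | 4.8 mg/kg | 3.2 mg/kg | Discontinue |
| -2 | 3.2 mg/kg | Discontinue | Discontinue |

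The line below it reads: "Subjects will be withdrawn from the study treatment if further toxicity meeting the requirement for dose reduction occurs".

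Section 6.5 limits dose modification to TEAEs that the investigator judges drug-related. It allows case-by-case exceptions if the investigator and sponsor agree and the agreement is documented.

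**The concern.** The sentence on further increases names Cycle 1. A bar on increasing the dose does something for a Cycle 1 event only if the subject is dosed again. The 3.2 mg/kg column, which matches the Cycle 1 dose, says to stop. With about 135 sites planned (Section 4.1), the same event could be handled in two ways.

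The first stake is the treatment of the subjects concerned. The second is what Arm 2's safety data mean. Section 4.3 justifies the regimen by the hypothesis that a low first dose lowers the risk of early severe thrombocytopenia and neutropenia. Section 9.5.2 plans summaries of TEAEs by action taken, including discontinuation of study treatment. If sites act differently on Cycle 1 events, those summaries and the exposure data partly reflect how each site read the page.

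**Working it through.** **1. The texts side by side.**

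*Cycle 2 event (4.8 mg/kg given).* The 4.8 column gives 3.2 mg/kg, and the sentence bars a later increase. The two fit together.

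*Cycle 1 event (3.2 mg/kg given).* Three readings are open:

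- Level 0 is the dose at which the toxicity occurred. The 3.2 column gives Discontinue. The sentence is obeyed but has no work to do in Cycle 1.
- The sentence governs the first event. The subject continues without an increase, and the 3.2 column and the line under the table apply to a later event. This suits the word further in that line.
- Level 0 is the dose due next. The 4.8 column gives 3.2 mg/kg. Applied to Cycle 2, however, this reading uses the 6.4 column and returns 4.8 mg/kg, the dose just given, which sits badly with the general rule of going down one level. It is the weakest reading, but the table does not exclude it.

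Table 6.4 does not settle the matter. For a Grade 4 platelet decrease it calls for reduction by one level and resumption, and elsewhere (for example Grade 4 ocular events) it lists discontinuation as a separate action. A Cycle 1 subject in Arm 2 cannot both resume and follow the 3.2 column. The provision for exceptions does not state the default.

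**2. The plan's own ORR figure.** Inputs from Sections 9.2 and 9.3: N = 210 per arm, null 26.4%, alternative 37%, two-sided 5%, success when the Clopper-Pearson lower bound exceeds 26.4%.

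- 68/210: lower bound 26.10%, fails. 69/210: lower bound 26.55%, passes.
- P(X ≥ 69 | 210, 0.264) = 0.0222.
- P(X ≥ 69 | 210, 0.37) = 0.9066, which agrees with the stated 91%.

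**3. A bound on the ORR effect.** Let f be the share of Arm 2 subjects with a reduction-level, drug-related TEAE in Cycle 1. The documents do not give f, so 1% to 10% is assumed. The comparison is with all of them continuing and responding at 37%.

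- If all stop and none responds: ORR = 0.37 × (1 − f).
- If all stop and respond at half the rate: ORR = 0.37 × (1 − f/2).
- Power = P(X ≥ 69 | 210, ORR).

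| f | Subjects (210 × f) | ORR, none responds | Power | ORR, half rate | Power |
|---|---|---|---|---|---|
| 0 | 0 | 37.0% | 90.7% | 37.0% | 90.7% |
| 1% | 2.1 | 36.6% | 88.7% | 36.8% | 89.7% |
| 2% | 4.2 | 36.3% | 86.4% | 36.6% | 88.7% |
| 5% | 10.5 | 35.2% | 77.8% | 36.1% | 85.2% |
| 10% | 21 | 33.3% | 58.0% | 35.2% | 77.8% |

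The largest gap between readings is 0.37 × f: 0.4, 0.7, 1.9 and 3.7 points.

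**4. Does stopping mean non-response?** The Efficacy Analysis Set keeps everyone dosed once, and Section 9.5.1.1 counts a not-evaluable BOR as non-response. Sections 4.1.1 and 8.3 continue scans after stopping, and Section 9.5.1.1 counts response until progression or new anticancer treatment. A stopped subject can therefore still be a responder. Appendix 4 (Section 10.4), by contrast, ends BOR at EOT. Suppose the decision to stop is taken when Cycle 2 is due, at 21 days. The EOT visit then falls by 21 + 7 = 28 days. The earliest scheduled scan is at 42 − 7 = 35 days, with confirmation at least 28 days later. Under Appendix 4 that subject could not have a confirmed response.

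**The case against.** A reader might infer a flat contradiction. The documents do not support that. The sentence immediately before the quoted one sends Arm 2 to Table 6.3, and a site that discontinues breaks no rule, since it does not increase the dose. The reference to Cycles 1 or 2 may simply explain what up-titration means. Moreover, repeating 3.2 mg/kg is hard to call a reduction. All of this stands, so continued dosing is an implication and not an instruction. It does not remove the ambiguity, because the Cycle 1 wording and the line about further toxicity still point the other way.

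A reader might also infer that Arm 2's ORR depends on which text a site follows. That is not shown:

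- The event rate is missing. Table 4.2 counts Grade 3 or higher events in 12 breast cancer subjects without the cycle, and many such events do not require reduction: Table 6.4 resumes dosing after Grade 3 neutropenia.
- The remark in Section 4.3 that "Grade 3 or 4 thrombocytopenia was observed most often in Cycle 1" describes the dose escalation that led to the up-titration idea, not Cycle 1 at 3.2 mg/kg. Section 2.2 reports no dose-limiting toxicities in the 3.2 mg/kg cohort, whose size is not given.
- The bound assumes that subjects kept at a low dose respond at 37%, although none of the six confirmed responses in Section 2.2 was at 3.2 mg/kg. Its least favourable column also assumes that stopped subjects never respond.
- It contrasts all stopping with all continuing, not mixed practice.

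Nor does the general rule send Arm 2 to the wrong table. Its cross-reference is incomplete, but the same subsection limits Table 6.2 to the fixed-dose arm and gives Arm 2 its own table. Finally, no formal arm comparison is planned, regimen selection rests on study U31402-A-U102, and Arm 1's test is untouched.

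**Conclusion.** The ambiguity is real and confined to Arm 2 subjects with a drug-related TEAE requiring dose reduction in Cycle 1. For them the protocol supports both continuing and permanently stopping, and does not say which is the default. The direct consequences are for their treatment and for Arm 2's discontinuation, exposure and tolerability summaries.

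An ORR effect is possible but unquantified. The losses of 0.7 to 3.7 points at f = 2% to 10%, with power falling to between 86.4% and 58.0%, are worst cases on assumed rates. Any real effect would also depend on which BOR window applies, where Section 9.5.1.1 and Appendix 4 differ. The point merits correction because it is cheap and bears on patient handling; it does not put the primary analysis in doubt.

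**What to change.** - Reconcile the Arm 2 text in Section 6.5 with Table 6.3, so that the sentence naming Cycle 1, the 3.2 mg/kg column and the line under the table give one instruction. Which clinical rule that is rests with the sponsor's clinical team.
- Define level 0 in Table 6.3, and label the columns by cycle if that is what is meant.
- Add Table 6.3 to the general cross-reference in the Dose Reduction Guidelines.
- In the SAP, tabulate Arm 2 subjects with a reduction-level, drug-related TEAE in Cycle 1 by action taken, so that any mixed handling before the clarification is visible.

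The cost is a clarification letter or short amendment, and one table from data already recorded on the AE and drug administration eCRF pages.
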